#### Table 5 Recommended Management of Cases of Vitreous Hemorrhage

 ${\sf BCVA} = {\sf best-corrected visual acuity; } {\sf SD-OCT} = {\sf spectral-domain optical coherence tomography.}$ 

#### 5.1.5.5 Recommended Management of Conjunctival Retraction or Conjunctival Erosion Cases

The recommended management of patients with conjunctival retraction or conjunctival erosion is presented in Table 6.

# Table 6Recommended Management of Patients with Conjunctival
Retraction or Conjunctival Erosion

Event	Patient's Examination and Management Guidelines
Conjunctival Retraction	
 
Prescribe antibiotic drops as per standard of care.
 
Consult Medical Monitor for management.
 
Schedule for surgery as soon as possible.         
 
Perform conjunctival flap revision with robust undermining of the surrounding conjunctiva and Tenon's capsule and release of any traction from previous surgery before advancing healthy tissue to limbus.
 
Suture the flap with multiple interrupted sutures.
 
 
 
In case of recurrent conjunctival retraction, consider use of a split thickness corneal graft placed underneath the conjunctiva and Tenon's capsule (if corneal tissue is not available, consult Medical Monitor for advice on further management).
 

Conjunctival Erosion	
 
In case of confirmed or suspected conjunctival erosion, Prescribe antibiotic drops as per standard of care.
 
For a suspected conjunctival erosion, consider application of topical fluorescein over conjunctiva to confirm erosion on slit lamp examination using cobalt blue light.
 
Consult the Medical Monitor for management.
 
Watch and wait in case of small localized erosion without flange exposure if the surrounding tissue is well adhered to sclera and there is no evidence of an active leak.
 
Schedule for surgery in case of full-thickness erosion (i.e., exposing the flange), or evidence of an active leak with Seidel positivity.
 
Perform conjunctival flap revision with robust undermining of the surrounding conjunctiva and Tenon's capsule and release of any traction from previous surgery.
 
Suture the flap with multiple interrupted sutures.
 
In case of recurrent conjunctival erosion, consider use of a split thickness corneal graft placed underneath the conjunctiva and Tenon's capsule (if corneal tissue is not available, consult Medical Monitor for advice on further management).
 

## 5.1.5.6 Recommended Management of Conjunctival Bleb

The recommended management of patients with conjunctival bleb is presented in Table 7.

Timing of Occurrence	Patient's Examination and Management Guidelines
Post implant insertion	Perform Seidel test
surgery	
 
If positive, discuss with the Medical Monitor about potential surgery to revise conjunctiva/Tenon's capsule and sclerotomy.
 

	
 
If negative, continue with post-operative topical medications (Appendix 17), and follow regular visit schedule.
 

During a refill-exchange attempt	• If the implant septum is no longer visible, consider delaying the refill-exchange. Reattempt the refill-exchange after approximately 7 days once the bleb is resolved.
A month before a scheduled refill-exchange	
 
If the bleb has not resolved and the implant septum is not fully visible, perform retroillumination by shining a light towards the implant body through the dilated pupil
 

	
 
If the implant septum becomes illuminated with clear margins to provide adequate visibility, consider observation.
 

	
 
If the implant septum does not illuminate or its margins do not appear sufficiently defined, discuss with the Medical Monitor about potential surgery to revise the conjunctiva and excise the bleb, potentially in conjunction with the refill- exchange procedure.
 

# Table 7 Recommended Management of Patients with Conjunctival Bleb

# 5.1.5.7 Recommended Management of Endophthalmitis

The recommended management of patients with endophthalmitis is presented in Table 8.

Event	Patient's Examination and Management Guidelines
Endophthalmitis (implant arm)	• Perform vitreous tap and/or anterior chamber tap to obtain fluid specimen for culture. Send aqueous humor sample to local laboratory for microbiology cultures.
	
 
Treat with intravitreal vancomycin and ceftazidime or as per standard of care.
 

	
 
For patients with a PDS implant, perform a saline flush of implant contents using refill needle followed by a flush of the implant with 100 μL of vancomycin (1.0 mg/mL) using the refill needle.
 

	• Start antibiotic drop coverage per standard of care. Oral antibiotics may also be considered.
	• In certain circumstances, a pars plana vitrectomy should be considered, after consultation with the Medical Monitor.
	• Perform a safety assessment visit (unscheduled; see Appendix 4) daily after occurrence of endophthalmitis until the posterior segment of the eye improves with clearance of the vitreous debris. If possible, perform ocular B-scan ultrasonography.
	• For patients with a PDS implant, perform a refill-exchange procedure (with ranibizumab 100 mg/mL) after endophthalmitis resolves as determined by the investigator and after discussion with Medical Monitor.

#### Table 8 Recommended Management of Patients with Endophthalmitis

PDS = port delivery system with ranibizumab

# 5.1.5.8 Recommended Management of Device Dislocation

The recommended management of patients with device dislocation is presented in *Table 9*.

Type of dislocation	Patient's Examination and Management Guidelines
Into the vitreous cavity	The implant may dislocate in the anterior vitreous behind the scleral wound, with secondary vitreous fluid leak underneath the Tenon's capsule through the scleral wound. It is recommended to surgically remove the implant by performing a vitrectomy and implant removal procedure as soon as possible, after consultation with the Medical Monitor.
	Urgent surgical intervention is recommended if device dislocation is associated with the following events:
	Positive Seidel test
	Retinal detachment
	Appositional choroidal detachments
	• Dislocated implant resting on or near the macula
	Topical, intravitreal, and/or systemic treatment may also be needed per standard of care in case of ocular infections, intraocular inflammation, hypotony, or other associated events. Prophylactic treatment to limit the risk of ocular infections may be needed in some cases.
Outside the vitreous cavity	The implant may entirely dislocate or subluxate outside the vitreous cavity into or beyond the subconjunctival space. It is recommended to surgically intervene as soon as possible, after consultation with the Medical Monitor.
	• If the implant is subluxated into the subconjunctival space without extrusion through the conjunctiva and part of the implant body is still in the scleral wound, the implant may be seated back into its original position. The oversized scleral wound should be sutured to reduce its length to 3.5 mm to provide tight fit of the implant.
	• If the implant is entirely dislocated into the subconjunctival space, removal of the implant is recommended followed by closure of the scleral wound with non-resorbable sutures.
	Urgent surgical intervention is recommended if device dislocation is associated with the following events:
	• Conjunctival opening with vitreous leak and implant expulsion (open globe)
	Retinal detachment
	• Appositional choroidal detachments
	Topical, intravitreal, and/or systemic treatment may also be needed per standard of care in case of ocular infections, intraocular inflammation, hypotony, or other associated events. Prophylactic treatment to limit the risk of ocular infections may be needed in some cases.

## Table 9 Recommended Management of Patients with Device Dislocation

## 5.2 SAFETY PARAMETERS AND DEFINITIONS

Safety assessments will consist of monitoring and recording adverse events, including serious adverse events and adverse events of special interest, performing protocol-specified safety laboratory assessments, measuring protocol-specified vital signs, and conducting other protocol-specified tests that are deemed critical to the safety evaluation of the study.

Certain types of events require immediate reporting to the Sponsor, as outlined in Section 5.4.

## 5.2.1 Adverse Events

According to the ICH guideline for Good Clinical Practice, an adverse event is any untoward medical occurrence in a clinical investigation subject administered a pharmaceutical product, regardless of causal attribution. An adverse event can therefore be any of the following:

- Any unfavorable and unintended sign (including an abnormal laboratory finding), symptom, or disease temporally associated with the use of a medicinal product, whether or not considered related to the medicinal product
- Any new disease or exacerbation of an existing disease (a worsening in the character, frequency, or severity of a known condition) (see Sections 5.3.5.8 and 5.3.5.9 for more information)
- Recurrence of an intermittent medical condition (e.g., headache) not present at baseline
- Any deterioration in a laboratory value or other clinical test (e.g., ECG, X-ray) that is associated with symptoms or leads to a change in study treatment or concomitant treatment or discontinuation from study drug
- Adverse events that are related to a protocol-mandated intervention, including those that occur prior to assignment of study treatment (e.g., screening invasive procedures such as biopsies)

#### 5.2.2 Serious Adverse Events (Immediately Reportable to the Sponsor)

A serious adverse event is any adverse event that meets any of the following criteria:

- Is fatal (i.e., the adverse event actually causes or leads to death)
- Is life threatening (i.e., the adverse event, in the view of the investigator, places the patient at immediate risk of death)

This does not include any adverse event that, had it occurred in a more severe form or was allowed to continue, might have caused death.

• Requires or prolongs inpatient hospitalization (see Section 5.3.5.10)

- Results in persistent or significant disability/incapacity (i.e., the adverse event results in substantial disruption of the patient's ability to conduct normal life functions)
- Is a congenital anomaly/birth defect in a neonate/infant born to a mother exposed to study drug
- Is a significant medical event in the investigator's judgment (e.g., may jeopardize the patient or may require medical/surgical intervention to prevent one of the outcomes listed above)

The terms "severe" and "serious" are not synonymous. Severity refers to the intensity of an adverse event (e.g., rated as mild, moderate, or severe according to the adverse event severity scale; see Section 5.3.3, Table 10); the event itself may be of relatively minor medical significance (such as severe headache without any further findings).

Severity and seriousness need to be independently assessed for each adverse event recorded on the eCRF.

Serious adverse events are required to be reported by the investigator to the Sponsor immediately (i.e., no more than 24 hours after learning of the event; see Section 5.4.2 for reporting instructions).

#### 5.2.3 Adverse Events of Special Interest (Immediately Reportable to the Sponsor)

Adverse events of special interest are required to be reported by the investigator to the Sponsor immediately (i.e., no more than 24 hours after learning of the event; see Section 5.4.2 for reporting instructions). Adverse events of special interest for this study are as follows:

- Cases of potential drug-induced liver injury that include an elevated ALT or AST in combination with either an elevated bilirubin or clinical jaundice, as defined by Hy's Law (see Section 5.3.5.6)
- Suspected transmission of an infectious agent by the study drug, as defined below

Any organism, virus, or infectious particle (e.g., prion protein transmitting transmissible spongiform encephalopathy), pathogenic or non-pathogenic, is considered an infectious agent. A transmission of an infectious agent may be suspected from clinical symptoms or laboratory findings that indicate an infection in a patient exposed to a medicinal product. This term applies only when a contamination of the study drug is suspected.

- Sight-threatening adverse events: an adverse event is considered to be sight threatening if it is a serious adverse event (as defined in Section 5.2.2) and it meets one or more of the following criteria:
  - The adverse event causes a decrease of ≥30 letters in BCVA (compared with the last assessment of VA prior to the most recent treatment) lasting more than 1 hour.

- The adverse event requires surgical intervention (i.e., conventional surgery, vitrectomy, vitreous tap, or biopsy with intravitreal injection of anti-infective medications, or laser or retinal cryopexy with gas) to prevent permanent loss of sight.
- The adverse event is associated with severe intraocular inflammation (e.g., endophthalmitis, 4+ anterior chamber cell/flare or 4+ cells in the vitreous; see Appendix 7 for intraocular inflammation grading scales).

Note: Adverse events should be reported, listing the underlying cause (if known) of the event as the primary event term (see Section 5.3.5.2).

- Ocular adverse events of special interest, defined as any of the events listed below, regardless of whether they occur in the study eye or the fellow eye, in a patient randomized to the PDS arm or the intravitreal arm, or the AE causality:
  - Vitreous hemorrhage
  - Endophthalmitis
  - Retinal detachment
  - Conjunctival retraction
  - Conjunctival erosion
  - Conjunctival bleb or conjunctival filtering bleb leak
  - Hyphema
  - Cataract
  - Device dislocation

Refer to the PDS Investigator's Brochure for further information.

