#### **Test Product (Investigational Drug)**

Patients will have the implant (filled prior to implantation with approximately 20  $\mu$ L of the 100-mg/mL formulation of ranibizumab [approximately 2-mg dose of ranibizumab]) surgically inserted in the study eye at the Day 1 visit following their randomization visit. After the initial fill of the implant with ranibizumab, patients will receive implant refill-exchanges at fixed 24-week intervals.

At each refill-exchange, a volume of approximately 100  $\mu$ L ranibizumab will be injected in situ into the implant through the septum to exchange the remaining contents of the implant with newly introduced ranibizumab. The volume of newly introduced ranibizumab remaining in the implant after the refill-exchange procedure will be approximately 20  $\mu$ L. Missed implant refill-exchanges should be made up no later than the next scheduled study visit. If at the next scheduled study visit the implant refill-exchange cannot be performed, the investigator must contact the Sponsor for further discussion prior to administering future implant refill-exchanges. Subsequent refill-exchanges will be administered according to the study treatment schedule relative to Day 1 until patients complete the study.

A representative from the Sponsor or an affiliate of the Sponsor may be present during the study-specific PDS surgeries or procedures (initial filling, insertion, refill-exchanging, and/or explantation) and/or other PDS-related surgeries or procedures to provide technical support to investigators during the use of the PDS and/or to observe the procedures related to the PDS.

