#### Table 2 Dosing Guidelines during Run-in Period and at Screening Visit

Anti-VEGF = anti-vascular endothelial growth factor.

a Randomization and the Day 1 visits should be completed within 21–28 days (inclusive) after last ranibizumab dose in the study eye.

All patients will return for a randomization visit and the Day 1 visit within 21–28 days (inclusive) after their last ranibizumab dose.

Patients who are randomly allocated to the implant arm will have the implant (pre-filled with ranibizumab 100 mg/mL) surgically inserted on Day 1, which must occur 1–7 days (inclusive) after randomization (i.e., randomization and Day 1 visit assessments cannot be performed on the same day) and no later than 28 days from the last intravitreal ranibizumab 0.5 mg injection. If the implant insertion surgery (Day 1) cannot be completed within the visit window after randomization, the randomization visit assessments may be repeated and an additional intravitreal ranibizumab 0.5 mg injection may be required after discussion with the Sponsor. After Day 1, patients in the implant arm will have scheduled safety visit assessments on Days 2 and 7 ( $\pm$ 2 days) and will receive implant refill-exchanges with ranibizumab 100 mg/mL Q24W at Week 24 ( $\pm$ 7 days), Week 48 ( $\pm$ 7 days), and Week 72 ( $\pm$ 7 days).

Patients who are randomly allocated to the intravitreal arm will receive intravitreal ranibizumab 0.5 mg injections starting on Day 1, which is to be administered at the conclusion of the randomization visit (i.e., randomization and Day 1 visit assessments are performed on the same day). Patients will receive ranibizumab 0.5 mg, injected intravitreally Q4W ( $\pm$ 7 days) from Day 1 until Week 92.

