#### 4.3.2.1 Port Delivery System with Ranibizumab

Study investigators must adhere to study-specific implant initial filling, insertion, refillexchange, and explantation procedures as outlined in the PDS IFU document.

Patients will have the implant (filled prior to implantation with approximately 20  $\mu$ L of the 100-mg/mL formulation of ranibizumab [approximately 2-mg dose of ranibizumab]) surgically inserted in the study eye at the Day 1 visit following their randomization visit. After the initial fill of the implant with ranibizumab, patients will receive implant refillexchanges at fixed 24-week intervals.

At each refill-exchange, a volume of approximately 100  $\mu$ L ranibizumab will be injected in situ into the implant through the septum to exchange the remaining contents of the implant with newly introduced ranibizumab. The volume of newly introduced ranibizumab remaining in the implant after the refill-exchange procedure will be approximately 20  $\mu$ L. Missed implant refill-exchanges should be made up no later than

**Port Delivery System with Ranibizumab—F. Hoffmann-La Roche Ltd.** 56/Protocol GR40548, Version 5

the next scheduled study visit. If at the next scheduled study visit the implant refillexchange cannot be performed, the investigator must contact the Sponsor for further discussion prior to administering future implant refill-exchanges. Subsequent refillexchanges will be administered according to the study treatment schedule relative to Day 1 as outlined in Appendix 1 until patients complete the study.

A representative from the Sponsor or an affiliate of the Sponsor may be present during the study-specific PDS surgeries or procedures (initial filling, insertion, refill-exchange, and/or explantation) and/or other PDS-related surgeries or procedures to provide technical support to investigators during the use of the PDS and/or to observe the procedures related to the PDS.

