#### 4.7.1 Adverse Events

All verbatim AE terms will be coded using the latest version of Medical Dictionary for Regulatory Activities (MedDRA).

For safety analyses, unless otherwise specified, only treatment-emergent AEs will be included in the analyses. Treatment-emergent AEs will be defined as any new AEs reported or any worsening of an existing condition on or after the surgical insertion of the implant or the first intravitreal ranibizumab injection post randomization through the completion of the study or until a patient discontinues prematurely. Adverse events with missing onset date will be considered to be treatment emergent. Adverse events with partially missing onset date will also be included as treatment emergent when the month (if it was recorded) and the year occur on or later than the month and year of the study treatment start date.

Frequency tables, including patient incidence rates by treatment group, will be provided for the events listed below. For ocular AEs, events in the study eye and fellow eye will be summarized separately.

- Ocular AEs and serious adverse events (SAEs)
- Non-ocular AEs and SAEs
- Adverse events of special interest (AESI) defined as follows:
  - An AE considered to be sight threatening (see Section 5.2.3 of the Protocol)
  - Cases of potential drug-induced liver injury that include elevated alanine aminotransferase (ALT) or aspartate aminotransferase (AST) in combination with either an elevated bilirubin or clinical jaundice, as defined by Hy's Law (see Section 5.3.5.6 of the Protocol)
  - Suspected transmission of an infectious agent by the study drug
  - Ocular AESIs (formerly adverse events potentially related to PDS) defined as:
    - Vitreous hemorrhage
    - o Endophthalmitis
    - Retinal detachment
    - Conjunctival retraction
    - Conjunctival erosion
    - Conjunctival bleb or conjunctival filtering bleb leak
    - Hyphema
    - Cataract (includes Preferred Terms cataract, cataract nuclear, cataract cortical, and cataract subcapsular)
    - Device dislocation (added in Protocol v 5)
- AEs leading to discontinuation of study treatment
- Treatment related Ocular AEs and SAEs as determined by the Investigator
- Anti-Platelet Trialists Collaboration Events (APTCs) defined as:
- non-fatal stroke AEs defined by terms from the conditions associated with central nervous system haemorrhages and cerebrovascular accidents Standardized

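### The 30-letter sight-threatening criterion is measured from an undefined most recent treatment, so its reference vision is nominally 4 to 24 weeks old in the implant arm and about 4 weeks old in the intravitreal arm

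*Protocol*

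**What the plan says.** Protocol Section 5.2.3 lists sight-threatening events among the adverse events of special interest. An event qualifies if "it is a serious adverse event (as defined in Section 5.2.2) and it meets one or more of the following criteria". The first criterion is a BCVA loss of at least 30 letters caused by the event, "compared with the last assessment of VA prior to the most recent treatment", with the loss lasting more than 1 hour. The other two are a need for surgery to prevent permanent loss of sight, and severe intraocular inflammation.

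Treatment times differ by design (Protocol Sections 3.1 and 4.3.2). The implant is "surgically inserted on Day 1, which must occur 1–7 days (inclusive) after randomization", and afterwards "patients will receive implant refill-exchanges at fixed 24-week intervals", that is, at Weeks 24, 48 and 72. In the other arm, "Patients will receive ranibizumab 0.5 mg, injected intravitreally Q4W" from Day 1 to Week 92. Implant-arm patients may also receive supplemental injections at Weeks 16, 20, 40, 44, 64, 68, 88 and 92 (Section 5.1.5.3). Section 5.2.3 does not say whether these count as treatment, or whether the treatment meant is the last one before the event began or the last one before vision was tested.

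SAP Section 4.7.1 takes the definition over by reference ("An AE considered to be sight threatening (see Section 5.2.3 of the Protocol") and tabulates patient incidence by treatment group. Incidence, severity and duration of these events form a stated safety endpoint (Protocol Table 1).

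Two other letter-loss rules in the protocol do not depend on treatment dates. The BCVA row of Table 4 refers to the last BCVA, and the functional hemorrhage scale in Appendix 8 refers to the previous visit.

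**The concern.** A letter-loss criterion compares like with like between arms only if the reference vision is of similar age in both. Here the reference moves with the dosing schedule, and the dosing schedule is what was randomized. The same course of vision loss can therefore meet the criterion in one arm and miss it in the other. Part of any difference between arms in this category could then reflect how often each arm is treated. These events are rare and clinically important, so a few reclassified patients could change how the table reads.

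**Working it through.** The documents give no figure for this rule, so there is nothing to reproduce. The check compares the age of the reference by arm and then applies the same vision course to both.

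**Inputs.** Implant-arm treatment: Day 1 and Weeks 24, 48, 72. Intravitreal treatment: every 4 weeks from Day 1 to Week 92. BCVA: every 4 weeks in both arms, before treatment (Protocol Appendices 1 and 2). Visit windows: ±7 days. Implant-arm randomization BCVA: 1 to 7 days before Day 1, with no BCVA on Day 1.

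**Nominal age of the reference.** Age = visit week minus week of the last treatment before that visit, over the 24 visits from Week 4 to Week 96.

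| | Implant | Intravitreal |
|---|---|---|
| Ages (weeks) | 4, 8, 12, 16, 20, 24, repeated | 4 throughout |
| Mean | 84/6 = 14 | 4 |
| Visits above 4 weeks | 20 of 24 | 0 of 24 |
| Maximum with windows | 168 + 14 = 182 days | 28 + 14 = 42 days |

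**Departures from the schedule.** If supplemental injections count as treatment, a patient who receives them in every interval has a maximum of 16 to 20 weeks and a mean of 8 to 10.7 weeks. In the intravitreal arm missed injections are not made up (Section 4.3.2.2), so one miss gives a nominal 8 weeks. Interruption (Table 4) or discontinuation (Section 4.6.1) can lengthen it further.

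**Same course in both arms, reference moving with each treatment.**
- Steady loss of 10 letters per visit: implant arm 3 × 10 = 30 at Week 12, before the first supplemental visit; intravitreal arm never above 10 on schedule.
- Steady loss of 6 letters per visit: implant arm 5 × 6 = 30 at Week 20; intravitreal arm never above 6. If the loss is due to nAMD activity, it stands at 4 × 6 = 24 letters at Week 16, past the 15-letter supplemental criterion. If that injection counts, the Week 20 loss is 6 and the criterion is not met.
- Sudden loss of 30 letters from a stable level: met in both arms.
- Reversed direction: an implant eye that gained 10 letters since its refill and then loses 30 shows 30 − 10 = 20 and is missed. An intravitreal eye whose reference already includes the gain shows 30 and counts.

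**Reading the rule as the last treatment before onset.** Injections after onset no longer move the reference, so slow worsening after onset is treated alike. The reference can still be up to 24 weeks old at onset in the implant arm. An eye that drifted down 10 letters since its refill and then loses 20 reaches 10 + 20 = 30. With the same course in the intravitreal arm, and the drift complete before the last injection, the loss is 20.

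**Size from random variation.** Assume normal changes with mean zero and the pooled masked SDs in SAP Appendix 4. At 4 weeks, 30/7.3 = 4.1 SD, probability about 0.00002. At 16 weeks, 30/8.8 = 3.4 SD, about 0.0003. Both are small. The normal tail is probably too thin: the same memorandum shows a minimum change of −32 among 124 patients at Week 4, where 124 × 0.00002 = 0.0025 losses of that size would be expected.

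**The case against.** The strongest case on the other side is that little depends on this criterion. The event must be serious and must itself cause the loss, so drift unrelated to an event should not count. The surgery and inflammation criteria read the same in both arms. Vitreous hemorrhage, endophthalmitis, retinal detachment and cataract are events of special interest in either arm with no letter threshold, and hemorrhage is also presented on a scale tied to the previous visit. Slow losses in the comparator arm remain visible in the BCVA analyses over time and in the proportions losing fewer than 10 or 5 letters. All of this stands. It limits the size of the problem but does not remove it: the three criteria are alternatives, so an event that qualifies only on letters still depends on the age of the reference.

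Two stronger readings are tempting.
- A reader might divide 30 letters by the longest interval and infer that steady loss qualifies from 30/24 = 1.25 letters per week in the implant arm but only from 30/4 = 7.5 in the intravitreal arm. The lower figure fails for nAMD-driven loss if supplemental injections count: 16 × 1.25 = 20 letters are lost by Week 16, the injection resets the reference, and the requirement becomes 30/16 ≈ 1.9 letters per week.
- A reader might infer that slow losses cannot qualify in the intravitreal arm. They can when injections are missed, interrupted or stopped, when 30 letters fall within one interval, or under the onset reading.

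**Conclusion.** The point holds in a limited form. The criterion rests on an undefined term. On either reading of that term, the reference vision can be up to 24 weeks old by schedule in the implant arm, against about 4 weeks in the intravitreal arm. Serious events with loss building over more than one visit, or following earlier drift, can be classified differently by arm. The usual direction is towards more implant-arm events, but it can reverse, so the rule cannot be defended as uniformly conservative for the implant.

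The numerical effect is probably modest. That judgment rests on the seriousness and causation requirements and on the two unaffected criteria; the documents give no event counts to test it. A reader might also take this category to be the main safety comparison. The documents do not support that: it is one of several categories in descriptive tables, with no test or margin attached. The primary efficacy analysis is not touched.

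**What to change.** Leave the 24-hour reporting rule and the investigator-classified count unchanged. In SAP Section 4.7.1:

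1. State what counts as the most recent treatment, including whether supplemental injections do, and whether it means the last treatment before event onset.
2. Add one sensitivity table by arm for serious study-eye ocular adverse events. Apply the 30-letter threshold to the change from the last scheduled BCVA before onset to the worst recorded BCVA between onset and resolution. Take the reference from visits that both arms have (randomization, then every 4 weeks), because only the implant arm is also tested on Days 2 and 7. The nominal age of the reference is then 4 weeks or less in both arms.
3. Show change from baseline, if at all, as descriptive context; it mixes earlier disease change into the event.

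The cost is a few lines of SAP text and one derived table from BCVA already collected. State the limits beside it. Four-weekly BCVA cannot reproduce the 1-hour duration or the causal attribution, and the extra early implant-arm tests give more chances to record a low value. The Primary and Update CSRs were complete when this SAP version was written, so label the table as added afterwards. It supports the investigator classification and does not replace it.
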